6. TOXICITIES AND DOSE DELAYS/DOSE MODIFICATIONS

Guidelines for dose delays and dose modifications are described below, and applicable to the start of each cycle as well as during the cycle if treatment-related toxicities occur. Subjects enrolled in this study will be evaluated clinically and with standard laboratory tests before and at regular intervals during their participation in this study as specified in Study Calendar & Evaluations. The NCI Common Terminology Criteria for Adverse Events (CTCAE) v4 will be used to grade adverse events. Subjects will be evaluated for adverse events (all grades), serious adverse events, and adverse events requiring study drug interruption or discontinuation as specified in Study Calendar & Evaluations.

Dose modifications are always based on the dose used in the previous cycle.

The investigator may attribute each toxicity event to the vaccine, nivolumab, mFOLFOX6, or any component of the combination therapy. Reduction or holding of one agent and not the other agent is appropriate if, in the opinion of the investigator, the toxicity is related to one of the study drugs. For example, if mFOLFOX6 is held due to an AE attributed to that component or the combination, then the vaccine and/or Nivolumab may continue to be administered. The drug to which the investigator is attributing the AE must be documented. If there is more than a 2-day delay for any reason, administration of study drugs should be re-aligned so that the chemotherapy falls within +2 days with the next cycle.

6.1 mFOLFOX6

Contraindicated in: Hypersensitivity to oxaliplatin, severe renal impairment ($\text{CrCl} < 30 \text{ mL/min}$), pregnant/breastfeeding, peripheral neuropathy with severe functional impairment prior to the first cycle. Use caution in patients with: Previous pelvic radiotherapy, recent myocardial infarction, uncontrolled angina, uncontrolled hypertension, uncontrolled cardiac arrhythmias, uncontrolled congestive heart failure, baseline > 3 loose bowel movements per day (in patients without colostomy or ileostomy), symptomatic peripheral neuropathy. Toxicities include: myelosuppression \pm infection, neuropathy, nausea, vomiting, diarrhea, transaminitis, fatigue, mucositis, abdominal pain, bleeding, rash, hand-foot syndrome, pharyngolaryngeal dysesthesia, arterial or venous thromboembolism, venous occlusive disease, hypersensitivity reaction, cardiotoxicity, hemolytic uremic syndrome, nephrotoxicity, pancreatitis, pneumonitis, rhabdomyolysis, RPLS.

The following dose reductions should be used for all toxicities:

Agent	Dose Level 0	Dose Level -1	Dose Level -2	Dose Level -3
Oxaliplatin	85 mg/m ²	65 mg/m ²	50 mg/m ²	Discontinue
Leucovorin	400 mg/m ²	400 mg/m ²	400 mg/m ²	Discontinue
Fluorouracil bolus	400 mg/m ²	320 mg/m ²	260 mg/m ²	Discontinue
Fluorouracil	2400 mg/m ²	1900 mg/m ²	1500 mg/m ²	Discontinue

*Leucovorin is delayed or omitted if bolus fluorouracil is delayed or omitted

*Institutional standards for measuring height and weight during chemotherapy administration should be used and dose adjusted according to institutional standards.

6.1.1 Renal Impairment

mFOLFOX6 is contraindicated in severe renal impairment ($\text{CrCl} < 30 \text{ mL/min}$).

CrCl (mL/min)	Oxaliplatin	Leucovorin	Fluorouracil
50-80	No change	No change	No change
30-49	No change, monitor	No change	No change, monitor
<30	Discontinue	No change	Consider dose reduction to next lower dose level

6.1.2 Hepatic Impairment

Limited data are available regarding patients with hepatic impairment.

Bilirubin		AST/ALT	Oxaliplatin	Leucovorin	Fluorouracil
Bilirubin \leq 2 x ULN			No change	No change	Caution
Bilirubin > 2-4 x ULN	and/or	AST/ALT 2-4 x ULN	No change	No change	Caution
Bilirubin > 4 x ULN	and/or	AST/ALT > 4 x ULN	No data available	Omit if 5FU omitted	OMIT if bilirubin > 4 x ULN

6.1.3 Hematologic Toxicity

Neutropenia

Fever or other evidence of infection must be assessed promptly and treated aggressively.

Grade	ANC (x 10⁹/L)
1	≥ 1.2
2	1.0-1.19
3	0.5-0.99
4	< 0.5

*If ANC < 1.2 on day 1 of cycle, hold treatment and check weekly CBC

*If ANC ≥ 1.2 within 4 weeks, proceed at dose level across from nadir ANC

*If ANC remains < 1.2 after 4 weeks, discontinue treatment

Dose modification

Grade	Dose Level Subsequent Cycles	
	Oxaliplatin	Fluorouracil
1	Same dose level	Same dose level
2	Same dose level	Same dose level
3	Decrease 1 dose level	Same dose level
4	Decrease 1 dose level	Omit bolus Decrease CI 1 dose level
Neutropenic Fever	Omit until neutropenic fever resolves. Consider decreasing 2 dose levels.	
Sepsis/septic shock	Discontinue	Discontinue

Thrombocytopenia

Grade	Platelets (x 10⁹/L)
1	≥ 75
2	50-74.9
3	10-49.9
4	< 10

*If platelets < 75 on day 1 of cycle, hold treatment and check weekly CBC

*If platelets ≥ 75 within 4 weeks, proceed at dose level across from nadir platelet count

*If platelets remain < 75 after 4 weeks, discontinue treatment

Dose modification

Dose Level Subsequent Cycles		
Grade	Oxaliplatin	Fluorouracil
1	Same dose level	Same dose level
2	Same dose level	Same dose level
3	Decrease 1 dose level	Same dose level
4	Decrease 2 dose levels	Same dose level

6.1.4 Peripheral Sensory Neuropathy

Neuropathy may be partially or wholly reversible after discontinuation of therapy.

Grade	Symptoms
1	Asymptomatic Mild paresthesias Loss of deep tendon reflexes
2	Moderate symptoms Limiting instrumental ADLs
3	Severe symptoms Limiting self-care ADLs
4	Life-threatening consequences Urgent intervention indicated
5	Death

Dose modification

Dose Level Subsequent Cycles		
Grade	Oxaliplatin	Fluorouracil
1	Same dose level	Same dose level
2 (persistent)	Decrease 1 dose level	Same dose level
3	1st occurrence	Decrease 1 dose level
	2nd occurrence	Decrease 1 dose level
Persistent	Discontinue	Same dose level
4	Discontinue	Same dose level

*Patients with good recovery from Grade 3 neuropathy may be considered for re-challenge with oxaliplatin, with starting dose one level below that which they were receiving when neuropathy developed

6.1.5 Gastrointestinal Toxicity

mFOLFOX6 can cause nausea, vomiting, and diarrhea. Prophylactic and/or therapeutic anti-emetic and anti-diarrheal therapies are warranted. Caution is advised in patients with baseline of > 3 loose bowel movements per day. Severe diarrhea/emesis can result from the combination of oxaliplatin and 5FU. Dehydration, paralytic ileus, intestinal obstruction, hypokalemia, metabolic acidosis and renal failure may be caused by severe diarrhea/emesis. In patients with diarrhea, treatment should be delayed until symptoms reach a level of Grade 2 or less.

Grade	Symptoms
1	Increase < 4 stools per day over baseline Mild increase in ostomy output over baseline
2	Increase of 4-6 stools per day over baseline Moderate increase in ostomy output over baseline
3	Increase of \geq 7 stools per day over baseline Severe increase in ostomy output over baseline Incontinence Hospitalization indicated Limiting self-care ADLs
4	Life-threatening consequences Urgent intervention indicated
5	Death

6.1.6 Mucositis

In patients with mucositis, treatment with 5-FU should be delayed until symptoms reach a level of Grade 2 or less.

Grade	Symptoms
1	Asymptomatic or mild symptoms; Intervention not indicated
2	Moderate pain; Not interfering with oral intake; Modified diet indicated
3	Severe pain; Interfering with oral intake
4	Life-threatening consequences; Urgent intervention indicated
5	Death

6.1.7 Palmar-Plantar Erythrodysesthesia (Hand-Foot Syndrome)

This has been reported as an unusual complication of high dose bolus or protracted continuous therapy with fluorouracil causing redness, swelling, and pain on the palms of the hands and/or the soles of the feet, sometimes with blistering. Although less common, it may occur elsewhere on the skin such as the knees or elbows. Treatment is supportive including moisturizing creams, topical anti-inflammatory medications, and topical or oral pain relievers. Patients should limit the use of hot water, take cool showers or baths, pat skin dry/avoid rubbing of hands or feet, apply ice packs or cool wet towels, avoid the sun/sources of heat, avoid harsh chemicals, avoid walking barefoot and wear loose-fitting clothing.

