5.2.2.1 Oxaliplatin

- Oxaliplatin administration must always precede the administration of 5-FU.
- Oxaliplatin may be given at the same time as leucovorin in separate bags using a Y connector (providing trometamol is not used as an excipient).
- Oxaliplatin may not be administered with fluorouracil.
- Do not use with injection equipment containing aluminum, as this can degrade platinum compounds.
- Oxaliplatin causes irritation if extravasated (follow local policy).
- Acute neurotoxicity is common with oxaliplatin and can be precipitated on exposure to cold, therefore cryotherapy should be avoided.
- Infuse IV over 2 hours. Increasing infusion time to 6 hours may decrease acute toxicity such as pharyngolaryngeal dysesthesia.
- Unopened vials should be stored at 15-30°C; protect from light.

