5.5 Supportive Care

Anti- emetics: Moderate emetogenicity. Follow local anti-emetic policy.

Anti-diarrheals: Follow local anti-diarrheal policy.

Premedications for hypersensitivity: Not usually required unless the patient has had a previous hypersensitivity. H1 or H2 blockers or steroids as pre-medication or for chills/fever /rigor during the infusion if required.

Treatment of dermatologic reactions may include topical moisturizers (containing urea, salicylic acid or ammonium lactate), sunscreen (SPF>15 UVA/UVB), topical steroids (e.g. clobetasol), and topical (e.g. lidocaine) and/or oral pain relievers (e.g. ibuprofen, naproxen, or celecoxib). Advise patients to limit the use of hot water, take cool showers or baths, pat skin dry/avoid rubbing of hands or feet, apply ice packs or cool wet towels, avoid the sun/sources of heat, avoid harsh chemicals, avoid walking barefoot and wear loose-fitting clothing.

Mouthwashes (e.g. Caphasol, grade III mouthwash) may be prescribed for mucositis to be used as needed.

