6.1.8 Pharyngolaryngeal Dysesthesia

Acute pharyngolaryngeal dysesthesia occurs in 1-2% of patients. It is characterized by subjective sensations of dysphagia and dyspnea without objective evidence of respiratory distress, laryngospasm or bronchospasm (e.g. cyanosis, hypoxia, wheezing, stridor). Symptoms are often precipitated by exposure to cold. The symptoms are rapidly reversible in the absence of treatment, but antihistamines and bronchodilators may be administered. Increasing the infusion time from 2 to 6 hours helps reduce the incidence of this syndrome.

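### The skin-care advice in 5.5 and 6.1.7 offers ice packs without excepting patients on oxaliplatin, although 5.2.2.1 says to avoid cryotherapy because cold can trigger oxaliplatin neurotoxicity

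*Combined protocol and SAP*

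**What the plan says.** Section 5.2.2.1, in its list of oxaliplatin instructions, warns: "Acute neurotoxicity is common with oxaliplatin and can be precipitated on exposure to cold, therefore cryotherapy should be avoided". Section 6.1.8, on pharyngolaryngeal dysesthesia, names the same trigger: "Symptoms are often precipitated by exposure to cold".

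Two other sections recommend cooling for skin problems:

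- **Section 5.5 (Supportive Care)** opens its skin paragraph with "Treatment of dermatologic reactions may include topical moisturizers", then lists what patients should be advised to do, including: "apply ice packs or cool wet towels, avoid the sun/sources of heat, avoid harsh chemicals".
- **Section 6.1.7 (hand-foot syndrome)** tells patients directly: "Patients should limit the use of hot water, take cool showers or baths, pat skin dry/avoid rubbing of hands or feet, apply ice packs". The sentence goes on to give cool wet towels as the alternative to ice packs. On the cause of the syndrome, the section says: "This has been reported as an unusual complication of high dose bolus or protracted continuous therapy with fluorouracil".

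Neither 5.5 nor 6.1.7 mentions oxaliplatin, sets a time limit relative to its infusion, or refers to 5.2.2.1 or 6.1.8.

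**The concern.** The plan identifies cold as a trigger for a toxicity it calls common, and elsewhere offers a cold application to patients who will often be receiving the drug concerned. Someone who opens only the supportive-care or hand-foot section, perhaps to write patient instructions, would not learn of the oxaliplatin warning. Patients carry out this advice themselves, so it should be safe as written.

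What is at stake is avoidable cold-triggered symptoms in some patients during chemotherapy.

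**Working it through.** No arithmetic applies, because the plan states no figure on this point. The check is whether the instructions can apply to the same patient at the same time, and whether any text reconciles them.

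1. **Does the regimen combine the two drugs?** Yes. The table in 5.2.2 gives oxaliplatin, leucovorin, bolus fluorouracil and a 46-hour fluorouracil infusion as one mFOLFOX6 regimen. Section 5.2.1 schedules it every 14 days, for 4 cycles before surgery and 8 after. Both arms receive it (5.1.2 and 5.1.4).

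2. **Does the skin advice concern this regimen?** Yes. Section 6.1.7 sits within 6.1, the mFOLFOX6 toxicity section, and attributes the syndrome to fluorouracil. The introduction to 6.1 lists neuropathy, hand-foot syndrome and pharyngolaryngeal dysesthesia together as toxicities of the regimen. Hand-foot syndrome will therefore usually arise while the patient's cycles include oxaliplatin.

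3. **Is the cold-triggered dysesthesia in 6.1.8 an oxaliplatin effect?** Section 6.1.8 does not name the drug. Section 5.2.2.1 makes the link: it says that lengthening the oxaliplatin infusion may reduce acute toxicity of this kind.

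4. **Does other text reconcile the instructions?** None was found. Section 6.1.4 (peripheral sensory neuropathy) covers grading, dose changes and re-challenge, with no rule on cold. Section 6.1.8 names the trigger but sets no restriction. Section 10.2 adds nothing on cold exposure.

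5. **When is there no conflict?** In two situations:
   - Oxaliplatin has been stopped while fluorouracil continues. Section 6.1.4 allows this: for persistent grade 3 or grade 4 neuropathy it discontinues oxaliplatin and keeps fluorouracil at the same dose level.
   - The patient is in maintenance, which contains no chemotherapy (5.1.5). Nivolumab rash (6.3.5) at that stage is an example.

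6. **Which cooling measures conflict?** Ice packs come closest to what 5.2.2.1 prohibits. Cool showers, baths and wet towels are at most a weaker case, because that section prohibits cryotherapy and mentions cold exposure only as the reason.

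**The case against.** The best defence has four parts.

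- **The prohibition is narrow and undefined.** Section 5.2.2.1 names cryotherapy, does not define it, and places it among rules on drug sequence, infusion equipment, extravasation and vial storage. It could mean only therapeutic cooling around the infusion, whereas 6.1.7 describes later self-care for a skin reaction. This doubt stands and limits how firmly the conflict can be stated. Against it, the reason given is exposure to cold, and that reason also covers an ice pack on the hands or feet.

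- **Nothing forces a site into conflict.** Section 5.5 introduces its treatments as options, and both sections offer towels instead of ice. This also stands. A reader might infer that the protocol requires cold treatment it has forbidden, but the wording only permits it. The weakness is that neither skin-care section tells the reader why towels would be the better choice.

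- **Sites may have other guidance.** Sections 5.2.1 and 10.2 refer to package inserts, and 5.2.1 also refers to institutional standards. Those sources are not available here, so whether they close the gap is unknown. They do not change what the protocol's own advice says.

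- **The harm is slight.** Of the dysesthesia, section 6.1.8 says: "The symptoms are rapidly reversible in the absence of treatment, but antihistamines and bronchodilators may be administered". It also describes the sensations as subjective, and it does not say that a pack on the hands or feet provokes them. Section 6.1.7 calls hand-foot syndrome unusual. These points are accepted and are why the matter is minor.

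**Conclusion.** The inconsistency is real and minor. Two sections offer ice packs without qualification to patients who will usually be on a drug for which another section says to avoid cryotherapy. The conclusion rests on one reading: that an ice pack falls within cryotherapy, or at least within the stated reason for avoiding it. The text supports that reading without settling it.

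Three stronger conclusions might be drawn, and the documents support none of them:

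- **A count of patients or cycles at risk.** A reader might treat every mFOLFOX6 cycle as exposed. The schedule does not measure harm. Exposure needs a skin reaction, concurrent oxaliplatin and a choice of ice over towels. The documents do not say how often ice would be chosen or how long after infusion the cold risk lasts, and oxaliplatin may be stopped early.
- **An effect on dose intensity or results.** A reader might expect cold-triggered symptoms to lead to oxaliplatin reductions under 6.1.4. No passage makes that link. Both arms receive the same chemotherapy and the same advice, so there is no basis for claiming an effect on the arm comparison, power or any other statistical quantity.
- **A ban on all cooling.** Section 5.2.2.1 does not say this, and there is no conflict for patients off oxaliplatin.

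**What to change.** Keep the present advice and add the following to both 5.5 and 6.1.7:

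*Do not use ice packs in patients whose current mFOLFOX6 cycles include oxaliplatin (see 5.2.2.1 and 6.1.8); use the other listed measures instead. Ice packs may be used once oxaliplatin has been discontinued or completed, including during maintenance.*

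Tying the restriction to the patient's current cycles avoids having to set a post-infusion window, for which the documents give no length. It also covers the patient who stays on fluorouracil after oxaliplatin stops.

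The cost is a short insertion in two sections, with no added visits, procedures or analyses. The downside is slightly less cooling relief during oxaliplatin cycles. Other treatment remains; for hand-foot syndrome, 6.1.7 states: "Treatment is supportive including moisturizing creams, topical anti-inflammatory medications, and topical or oral pain relievers". Section 5.5 likewise lists moisturizers, topical steroids and pain relievers. Patients off oxaliplatin lose nothing.

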6.1.8 Pharyngolaryngeal Dysesthesia

Acute pharyngolaryngeal dysesthesia occurs in 1-2% of patients. It is characterized by subjective sensations of dysphagia and dyspnea without objective evidence of respiratory distress, laryngospasm or bronchospasm (e.g. cyanosis, hypoxia, wheezing, stridor). Symptoms are often precipitated by exposure to cold. The symptoms are rapidly reversible in the absence of treatment, but antihistamines and bronchodilators may be administered. Increasing the infusion time from 2 to 6 hours helps reduce the incidence of this syndrome.

6.1.9 Venous Occlusive Disease

This is a rare but serious complication that has been reported in 0.02% of patients receiving oxaliplatin in combination with fluorouracil. VOD can lead to hepatomegaly, splenomegaly, portal hypertension and esophageal varices. Patients should be instructed to report any jaundice, ascites, or hematemesis immediately.

6.1.10 Hypersensitivity Reaction

Patients may experience platinum hypersensitivity. Special surveillance must be ensured for patients with a history of allergic manifestations to other products containing platinum. Therapies to treat anaphylaxis must be present when chemotherapy is administered. In the case of anaphylactic manifestations, the infusion should be interrupted immediately and appropriate symptomatic treatment started. Re-administration of oxaliplatin is contraindicated.

6.1.11 Cardiotoxicity

Cardiotoxicity, particularly angina and myocardial ischemia/infarction, is a serious complication of treatment with fluorouracil. Patients should be monitored carefully during therapy, particularly those with a prior history of cardiac disease or other risk factors. Patients with a history of cardiac disease should have a baseline ECG prior to starting therapy.

6.1.12 Hemolytic Uremic Syndrome (HUS)

HUS should be suspected and oxaliplatin therapy interrupted when hematocrit is < 25%, platelets < 100,000, and creatinine \geq 1.5 mg/dL. If HUS is confirmed, oxaliplatin should be permanently discontinued.

6.1.13 Pneumonitis

In the event of unexplained respiratory symptoms (e.g. non-productive cough, dyspnea, crackles or radiological pulmonary infiltrates), discontinue oxaliplatin until interstitial lung disease (ILD), pneumonitis or pulmonary fibrosis is excluded.

6.1.14 Additional Considerations

Dihydropyrimidine dehydrogenase (DPD) deficiency

Deficiency in the dihydropyrimidine dehydrogenase enzyme can cause rare, life-threatening toxicities (e.g. stomatitis/mucositis, neutropenia, neurotoxicity, and diarrhea) following the administration of fluorouracil. Severe, unexplained toxicities require further investigation prior to continuing treatment.

Drug Interactions

- Fluorouracil administration can cause marked elevations of prothrombin time (PT) and INR in patients stabilized on warfarin therapy. Monitor PT/INR at baseline and as clinically indicated while on therapy.
- Concurrent administration of fluorouracil and phenytoin may result in increased serum levels of phenytoin. Caution in patients with seizure disorders on phenytoin therapy.
- Caution when administering fluorouracil in conjunction with medications that may affect dihydropyrimidine dehydrogenase levels/activity.

Please see individual FDA package inserts for full drug interaction information.

6.2 CV301

In all completed and ongoing clinical trials, vaccinations with MVA-BN have shown to be generally safe and well tolerated. No cases of death, assessed as being even possibly related, have been reported for a subject in a clinical trial using MVA-BN. Results obtained from completed Phase 1 and 2 trials and ongoing trials with several recombinant MVA-BN based vaccines in healthy adults and children, HIV infected and cancer subjects demonstrate a similar safety profile as MVA-BN alone. Additional information on the safety profile of MVA-BN and recombinant MVA-based vaccines is provided in the Investigator's Brochure.

There are no dose modifications for CV301. In the case of an allergic reaction or an autoimmune response causing a serious adverse event thought to be related by the investigator to CV301, treatment would be stopped.

6.3 Nivolumab

There will be no dose escalations or reductions of nivolumab allowed. Premedications are not recommended for the first dose of nivolumab. Participants should be carefully monitored for infusion reactions during nivolumab administration. Doses of nivolumab may be interrupted, delayed, or discontinued depending on how well the participant tolerates the treatment. Guidelines on the recommended management are provided in the Investigator Brochure.

Nivolumab administration should be delayed for the following:

- Given hepatic involvement as an inclusion criteria, continue, withhold or permanently discontinue nivolumab based on the severity of hepatitis and baseline AST and ALT levels (following guidelines for use of nivolumab in HCC liver disease):
 - If AST/ALT is within normal limits at baseline and increases to > 3-5x the ULN, withhold dose
 - If AST/ALT is > 1-3x ULN at baseline and increases to > 5-8x the ULN, withhold dose
 - If AST/ALT is > 3-5x ULN at baseline and increases to > 8x the ULN, withhold dose
- Grade 2 non-skin, drug-related AE, with the exception of fatigue
- Grade 2 drug-related creatinine abnormalities
- Grade 3 skin, drug-related AE
- Grade 3 drug-related laboratory abnormality, with the following exceptions:
 - Grade 3 lymphopenia or asymptomatic amylase or lipase does not require dose delay

- Any adverse event, laboratory abnormality, or intercurrent illness which, in the judgment of the investigator, warrants delaying the dose of study medication.

Participants who require delay of nivolumab should be re-evaluated weekly or more frequently if clinically indicated and resume nivolumab dosing when re-treatment criteria are met. In general, in the event of a grade 2 AE, treatment with nivolumab can be resumed when the AE has resolved to \leq grade 1.

Nivolumab treatment should be permanently discontinued for the following:

- If AST/ALT increases to $> 10x$ the ULN or total bilirubin increases to $> 3x$ ULN, permanently discontinue (following guidelines for use of nivolumab in HCC liver disease).
- Any Grade 2 drug-related uveitis, eye pain or blurred vision that does not respond to topical therapy and does not improve to Grade 1 severity within the re-treatment period OR requires systemic treatment
- Any Grade 3 non-skin, drug-related AE lasting > 7 days or recurs, with the following exceptions for laboratory abnormalities, drug-related uveitis, pneumonitis, bronchospasm, neurologic toxicity, hypersensitivity reactions, infusion reactions, and endocrinopathies:
 - Grade 3 drug-related uveitis, pneumonitis, bronchospasm, neurologic toxicity, hypersensitivity reaction, or infusion reaction of any duration requires discontinuation
 - Grade 3 drug-related endocrinopathies, adequately controlled with only physiologic hormone replacement do not require discontinuation. Adrenal insufficiency requires discontinuation regardless of control with hormone replacement.
 - Grade 3 drug-related laboratory abnormalities do not require treatment discontinuation except:
 - Grade 3 drug-related thrombocytopenia > 7 days or associated with bleeding requires discontinuation

